8.2 Per Protocol

The Per-Protocol (PP) Population includes subjects in the ITT Population who do not have significant protocol deviations and who complete the study. Protocol deviations will be assessed prior to database lock and unmasking. Subjects in the PP Population will be analyzed as treated.

8.3 Safety

The Safety Population includes all randomized subjects who receive at least one dose of investigational product.

9. General Statistical Considerations

9.1 Unit of Analysis

Safety endpoints will be analyzed for both eyes will be made on samples pooled sector resulting in a single measurement for each subject and time point. Conjunctival redness, Schirmer's Test, and ocular discomfort scores from the Ora Calibra Ocular Discomfort Scale will be collected and analyzed for each eye. Eye dryness from the Visual Analog Scale (VAS) and Ocular Discomfort & 4-Symptom Questionnaire scores will be collected at the subject level Ocular itching from the Ora Calibra[®] Conjunctival Allergen Challenge will be collected in both eyes and analyzed sector from the Ora Calibra[®]. Assessment scales are detailed in the appendices of the study protocol.

9.2 Missing or Inconclusive Data Handling

Partial/missing start and end dates for AEs and concomitant medications required to flag data as treatmentemergent or concomitant with treatment will be imputed as follows:

Partial/missing start date:

- Dates with missing day only will be imputed as the 1st of the month unless the month and year are same as the month and year of first dose of study medication, in which case missing day will be imputed as the first dose day of study medication.
- Dates with both day and month missing will be imputed as 1 Jan unless the year is same as the year of first dose of study medication, in which case missing day and month will be imputed as the first dose day and month of study medication.
- Completely missing dates will be imputed as the first dose date of study medication unless the end date is on or before the first dose date of study medication, in which case missing date will be imputed as 1 Jan of the same year as the end date.

Partial/missing end date:

- Dates with missing day only will be imputed as the last day of the month unless the month and year are the same as the month and year of the last dose of study medication, in which case missing day will be imputed as the last dose day of study medication.
- Dates with both day and month missing will be imputed as 31 Dec unless the year is same as the year of the last dose of study medication, in which case missing day and month will be imputed as the last dose day and month of study medication.
- If the ongoing flag is missing or "Yes" then the date will not be imputed unless death date is available, in which case the missing date will be imputed as the death date. If ongoing is "No" then the missing end date will be imputed as the last dose date.
- If the imputed date is after the date of death, then the end date will be set equal to the date of death.

The original dates will be displayed in data listings and the imputed dates will be used in derivations only (study day, treatment-emergence status, etc).

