#### 8.3 Examination Procedures

8.3.1 Procedures to be Performed at the Study Visit with Regard to Study Objective(s)

Visit 1 (Day -14 -16/+2, Screening)

- Informed Consent and HIPAA
- Demographics
- Medical/Medication & Ocular History
- Urine Pregnancy Test (as needed)
- Symptom Questionnaires:
  - Ocular Discomfort & 4-Symptom Questionnaire
  - Ora Calibra® Ocular Discomfort Scale
  - Ocular Dryness Visual Analog Scale
  - Ora Calibra® Conjunctival Allergen Challenge Ocular Itching Scale
- Visual Acuity (ETDRS)

- Slit Lamp Biomicroscopy with Conjunctival Redness assessment
- Fluorescein Staining using the Ora Calibra® Corneal and Conjunctival Staining Scale
- Inclusion/Exclusion Criteria Review
- In-Office Vehicle Instillation by trained site staff

CAE Ex	posure		
	_		

• Slit Lamp Biomicroscopy with Conjunctival Redness assessment

- Schirmer's Test
- Intraocular Pressure
- Dilated Exam
- Schedule for Visit 2

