16.1 Adverse Events

For the purposes of this trial, an AE is defined as any untoward medical event occurring after the subject's signing of the informed consent until they are exited from the trial. An AE can therefore be any unfavorable and unintended sign, symptom, or disease occurring after the subject started the clinical trial, without any judgment about causality. Any pre-existing medical condition that worsens during the trial will also be considered a new AE. Documentation regarding the AE should be made as to the nature, date of onset, end date, severity, relationship to study procedure, expectedness, action(s) taken, seriousness, and outcome of any sign or symptom observed by the investigator or reported by the patient upon indirect questioning.

All AEs will be coded using the MedDRA Version 23.1.

Treatment-emergent adverse events (TEAEs) are defined as any event that occurs or worsens on or after the day that randomized study treatment is initiated. Adverse events recorded in the eCRF which began prior to treatment will not be included in the summary tables but will be included in the AE data listings.

An overall summary will be presented that includes the number and percentage of subjects who experienced at least one AEs, ocular AEs, non-ocular AEs, SAEs, AEs by maximal severity, AEs by relationship to study procedure, AEs leading to treatment discontinuation, and AEs resulting in death by treatment arm for the Safety Population. In addition, overall TEAEs and the number and percentage of subjects who experienced at least one TEAE, ocular TEAEs, non-ocular TEAEs, TE-SAEs, TEAEs by maximal severity, TEAEs by relationship to study procedure, TEAEs leading to treatment discontinuation, and TEAEs resulting in death by treatment arm for the Safety Population.

Separate summaries will be provided for the following categories of AEs:

- Ocular AEs by SOC and PT
- Non-ocular AEs by SOC and PT
- Ocular TEAEs by SOC and PT
- Non-ocular TEAEs by SOC and PT
- Instillation Site Ocular TEAEs by Duration of Time
- Ocular TEAEs by SOC, PT, and maximal severity
- Non-ocular TEAEs by SOC, PT, and maximal severity
- Ocular TEAEs by SOC, PT, and strongest relationship to study procedure
- Non-ocular TEAEs by SOC, PT, and strongest relationship to study procedure
- Ocular TEAEs by SOC, PT, maximal severity, and strongest relationship to study procedure
- Non-ocular TEAEs by SOC, PT, maximal severity, and strongest relationship to study procedure

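### Two partial start-date rules in SAP 9.2 ignore the end date, so an adverse event that resolved before first dose can be given a later onset and counted as treatment-emergent

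*SAP*

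**What the plan says.** SAP 9.2 has three rules for incomplete start dates of adverse events and concomitant medications.

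- **Day missing.** The start is the 1st of the month "unless the month and year are same as the month and year of first dose of study medication"; if they match, "in which case missing day will be imputed as the first dose day of study medication".
- **Day and month missing.** The start is 1 January unless the year matches first dose, "in which case missing day and month will be imputed as the first dose day and month of study medication".
- **Completely missing.** The start is the first dose date "unless the end date is on or before the first dose date of study medication", and otherwise 1 January of the year of the end date.

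Only the third rule uses the end date. All three read as complete sentences, so redaction does not explain the difference. No later line in SAP 9.2 corrects an imputed start that falls after the end; the only cap stated concerns end dates after death.

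The imputed values matter because "the imputed dates will be used in derivations only (study day, treatment-emergence status, etc". SAP 16.1 collects "any untoward medical event occurring after the subject's signing of the informed consent until they are exited from the trial" and calls an event treatment-emergent if it occurs or worsens on or after the day randomised treatment starts. It also states: "Adverse events recorded in the eCRF which began prior to treatment will not be included in the summary tables".

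Protocol 8.3.1 schedules screening as "Visit 1 (Day -14 -16/+2, Screening".

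**The concern.** Events are recorded from consent, which comes well before Day 1, so some will start and finish before any randomised dose. Vehicle instillation and exposure to the controlled adverse environment at Visit 1 make such events foreseeable. If the start of such an event is partly recorded and its month or year matches first dose, the rule moves the onset to Day 1. The derived record then has an onset after its own resolution. Because the onset equals Day 1, it also meets the definition of a treatment-emergent event.

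The result is perverse: a wholly blank start date is classified correctly, while one with the month and year recorded is not. What is at stake is the accuracy of the treatment-emergent tables and the credibility of the derived dates. The same two rules can give a medication stopped before dosing a start date after its stop date.

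**Working it through.** The plan states no figure on this point, so there is none to reproduce. The check applies the rules literally.

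**Inputs**
- Rules: SAP 9.2. Treatment-emergent definition: SAP 16.1.
- Visit 1 window (Protocol 8.3.1; SAP 4.1, Table 1, which has no Day 0): −14 − 16 = Day −30 to −14 + 2 = Day −12. Visit 1 is therefore 12 to 30 days before Day 1, with 14 planned.
- Assumption: first dose means the first randomised dose on Day 1.

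**Worked example (assumed dates):** first dose 20 Nov 2021, event ended 10 Nov 2021.

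| Recorded start | Imputed as written | Treatment-emergent? | With end-date check | Treatment-emergent? |
|---|---|---|---|---|
| UN-Nov-2021 | 20 Nov 2021 (10 days after end) | Yes | 1 Nov 2021 | No |
| UN-UN-2021 | 20 Nov 2021 (10 days after end) | Yes | 1 Jan 2021 | No |
| Completely missing | 1 Jan 2021 | No | 1 Jan 2021 (rule unchanged) | No |

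**How often the calendar triggers it.** Let g be the number of days from Visit 1 to first dose. Assume that every first dose date in 2021 is equally likely, and every pair with start ≤ end between Visit 1 and the day before first dose.

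- Pairs per first dose date: g(g + 1)/2, which is 78, 105 and 465 for g = 12, 14 and 30. Times 365: 28,470, 38,325 and 169,725.
- Day missing, first dose on day D of the month: the start must fall in the same month, so m = min(g, D − 1) start days qualify and m(m + 1)/2 pairs are misflagged.
- Day and month missing: the same formula with m = min(g, k), where k is the number of days since 1 January (0 to 364).

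*Day missing, g = 14.* The first 15 dates of a month contribute 14 × 15 × 16/6 = 560 in total, and each later date contributes 105. A 31-day month gives 560 + 16 × 105 = 2,240; a 30-day month 560 + 15 × 105 = 2,135; February 560 + 13 × 105 = 1,925. Year: 7 × 2,240 + 4 × 2,135 + 1,925 = 26,145.

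*Day and month missing, g = 14.* 560 + (365 − 15) × 105 = 37,310.

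| g (days) | Day missing | Day and month missing | Either, with end-date check |
|---|---|---|---|
| 12 | 20,670/28,470 = 72.6% | 27,820/28,470 = 97.7% | 0 |
| 14 | 26,145/38,325 = 68.2% | 37,310/38,325 = 97.4% | 0 |
| 30 | 56,354/169,725 = 33.2% | 160,270/169,725 = 94.4% | 0 |

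Direct enumeration of the coded rules gives the same shares, and using 2022 instead of 2021 does not change them.

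**Dependence on the date (day missing).** For g = 30: 0/465 for first dose on 1 Nov, 28/465 on 8 Nov, 190/465 on 20 Nov and 435/465 on 30 Nov. For g = 14: 0/105 on 1 Nov, 28/105 (27%) on 8 Nov and 105/105 on 15 Nov. The day-missing error cannot occur when first dose is on the 1st of a month (12 of 365 dates). The day-and-month-missing error cannot occur when first dose is on 1 January.

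**Side checks.** For events starting on or after first dose, including ongoing ones, the end-date check changed 0 of 16 results examined. If first dose meant the Visit 1 vehicle instillation, an imputed onset after the end date would occur in 0 cases.

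**The case against.** **Imputation may not be needed here.** SAP 9.2 imputes only dates required to set a flag, and an event with a complete end date before Day 1 cannot be treatment-emergent. One could argue that no start date needs imputing. The completely-missing rule answers this: it imputes a start in exactly that situation, so the section expects imputation there.

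**First dose is undefined.** SAP 9.2 does not say which dose it means, and vehicle is instilled at Visit 1 (Protocol 7.1.4). This stands as a condition on the conclusion. The randomised dose is the better reading: SAP 16.1 anchors treatment emergence to randomised treatment, and the listings separate run-in instillation (16.2.5.1) from study drug instillation (16.2.5.2).

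**All-event tables exist as well.** SAP 16.1 also plans summaries of all adverse events beside the treatment-emergent ones, so its sentence excluding pre-treatment events is not wholly clear, and a misflagged event might be tabulated anyway. That softens the conflict but does not undo a false treatment-emergent flag.

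**Imputing to first dose is conservative.** That is a sound way to resolve uncertainty about timing. A known earlier end date removes the uncertainty, and the third rule accepts that logic.

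**The percentages can mislead.** This largely stands. They are conditional on an unusual record and average over dates on which the error is impossible and dates on which it is certain. A start known only to the year, for an event that began at most 30 days before Day 1, is hard to imagine when events are queried at Visit 2 before dosing.

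**The boundary differs.** The third rule applies to ends on or before first dose; the proposed exception applies only to ends before it. The difference is real, but the stricter wording is safer because an event ending on Day 1 stays treatment-emergent. The zero error after the change was shown for complete end dates only; partial end dates are outside this point.

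**Conclusion.** The two rules are wrong as written. For an event with a partial start date matching first dose and a known end before it, they produce an onset after resolution and a false treatment-emergent flag. This rests on first dose meaning the first randomised dose on Day 1. If the Visit 1 vehicle dose were meant, the error would not arise for adverse events.

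The practical impact is probably small. The documents give no number of partial dates, and few are likely in a study of about two to four weeks. The rules apply alike to both arms, original dates stay in the listings, and no efficacy analysis uses them. The calendar shares above show how readily the rule misfires once such a record exists; they are not event rates. This is a minor correction worth making because it is cheap and the derived dates are otherwise impossible.

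**What to change.** Add an end-date exception to the day-missing and day-and-month-missing start rules only. If the known end date is before the first randomised dose date, impute the start as the 1st of the recorded month (day missing) or 1 January of the recorded year (day and month missing), never later than the end date. Leave the completely-missing rule unchanged. The wording should name the first randomised dose, which also settles the undefined term in these two rules.

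The 1 January value can precede consent, but the completely-missing rule already uses that convention and imputed dates serve derivations only. The same edit corrects medications stopped before first dose.

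Cost: a short edit to two SAP bullets and the matching derivation code, made before unmasking. No new data are needed.

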#### 7.1.4 Instructions for Dispensation, Use, and Administration

- At Visit 1, qualified subjects will be assigned a vehicle kit. Subjects will use two vials from the kit for Visit 1 in-office doses. After use, vials will be placed into a zip locked bag labeled with subject's initials and screening number for accountability.
- At Visit 2, qualified subjects will be randomized and will be assigned a single kit of 2 pouch supply of Reproxalap Ophthalmic Solution 0.25% or Vehicle. Subjects will be dosed in office four times (QID) by trained site staff.
- At Visit 3, subjects will be dosed three times in-office from the same kit by trained site staff.
- Subjects will be instructed to close their eyes for two minutes after instillation.

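### SAP 9.2 gives an AE with no start date that ended on the first-dose day a pre-treatment onset, although SAP 16.1 counts first-dose-day events as treatment-emergent

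*SAP*

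**What the plan says.** SAP 9.2 (Missing or Inconclusive Data Handling) sets the default for a start date with no day, month or year: "Completely missing dates will be imputed as the first dose date of study medication". It then makes an exception based on the end date: "unless the end date is on or before the first dose date of study medication, in which case missing date will be imputed" as 1 January of the end-date year. The section closes by saying that listings show the original dates, while imputed dates feed derivations, including treatment-emergence status.

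The two partial-date rules in 9.2 have no end-date exception. If the known month and year, or the known year alone, match first dose, the missing parts are filled with the first dose date. Otherwise they go to the first of the month or to 1 January.

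SAP 16.1 (Adverse Events) defines a TEAE as "any event that occurs or worsens on or after the day that randomized study treatment is initiated". It adds that events "which began prior to treatment will not be included in the summary tables but will be included in the AE data listings". One of its planned summaries is "Instillation Site Ocular TEAEs by Duration of Time".

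On Day 1, Protocol 7.1.4 states: "Subjects will be dosed in office four times (QID) by trained site staff".

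**The concern.** The two SAP sections place the first-dose day on opposite sides of the treatment boundary. Section 16.1 works at day level and includes that day. The exception in 9.2 also works at day level, but it handles an event that ended that day as though it must have started before treatment.

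Day 1 is a day of repeated in-office dosing, so an event that ended on Day 1 may have begun after a randomised drop. A brief instillation-site reaction is the natural example, and the SAP gives such reactions their own table. If the onset date of such a reaction were not recorded, the rule would take it out of that table and the other TEAE summaries. For a Day 1 reaction the error has one direction: it removes a TEAE and cannot add one.

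**Working it through.** The plan states no figure on this point, so there is none to reproduce. The check applies the rules as written.

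**Inputs.** F is the first dose date, taken as the first randomised dose (Day 1). E is the end date and S the imputed start. The start-date rules come from SAP 9.2 and the TEAE rule from SAP 16.1. The documents give no enrolment dates, so F = 15 November 2021 is an illustrative assumption.

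**Rules.**
- Start completely missing: S = 1 January of the year of E if E ≤ F; otherwise S = F.
- Only the year known: S = F if it is the year of F; otherwise 1 January of the known year.
- Month and year known: S = F if both match F; otherwise the first of the known month.
- TEAE if S ≥ F.

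**Results.**

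| Start information | End date | S as written | TEAE as written | TEAE with 'before' |
|---|---|---|---|---|
| None | 14 Nov (Day -1) | 1 Jan 2021 | No | No |
| None | 15 Nov (Day 1) | 1 Jan 2021 | **No** | **Yes** (S = 15 Nov) |
| None | 16 Nov (Day 2) | 15 Nov 2021 | Yes | Yes |
| None | Missing | 15 Nov 2021 | Yes | Yes |
| Year 2021 only | 15 Nov (Day 1) | 15 Nov 2021 | Yes | Yes |
| November 2021, no day | 15 Nov (Day 1) | 15 Nov 2021 | Yes | Yes |

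15 November is day 319 of 2021, so the imputed onset lies 319 - 1 = 318 days before first dose. Rows 2, 5 and 6 describe the same event with different amounts of start-date information. It loses its TEAE flag only when all of that information is missing.

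**Dependence on the chosen date.** When E = F, S is 1 January of the year of F. This is earlier than F unless F is itself 1 January. Over an assumed range of first-dose dates from 12 October 2021 to 31 December 2022 (20 + 30 + 31 + 365 = 446 days), the event is non-TEAE on 445. The exception is 1 January 2022.

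**Whether the flag is right, by true onset, for a record with no start date and E = Day 1.**
- Began on Day 1 after a dose: the non-TEAE flag is wrong.
- Began on Day 1 before the first dose: the flag conflicts with the day-level definition in 16.1.
- Began before Day 1 and did not worsen on treatment: the flag is right.

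**Effect per record.** Protocol section 4 plans about 75 subjects per group. One subject wrongly dropped changes a group's TEAE incidence by at most 1/75 = 1.3 percentage points. If the number of such records is assumed to be 0 to 2 in the whole trial, the largest change, with both in one group, is 2/75 = 2.7 points and the smallest is zero.

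**The case against.** The strongest answer is that the trigger is very narrow. It needs a record with no start day, month or year but a full end date equal to Day 1. Site staff give the doses in the clinic, onset date is a required item for every event (Protocol 9.1), and the investigator reviews events promptly for completeness (Protocol 8.3.1, early termination text). Staff who know that a reaction ended on Day 1 will nearly always know that it began that day. This stands, and it is why the expected effect is small.

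Three stronger readings are tempting, and the documents do not support them.
- A reader might infer that every record with no start date and a Day 1 end date is misclassified. Some may have begun between consent and Day 1, for instance after the Visit 1 vehicle dose or chamber exposure, and the Visit 2 AE query is listed before the first randomised dose. For those the flag is correct.
- A reader might infer that the rule removes same-day drop reactions in general. A reaction with a recorded onset is untouched, as is one with a partial onset date that matches first dose.
- A reader might weigh Day 1 by its share of all randomised doses. The documents disagree on Day 2 dosing (one administration in the synopsis; three in Protocol 7.1.4 and 8.3.1), so no share can be stated until they are reconciled. The point does not need one.

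It can also be said that the record is not lost. It stays in the AE listings with its original dates, and a separately dated worsening could still qualify it as a TEAE. Section 16.1 also plans tables of all AEs. Because the same section keeps events that began before treatment out of summary tables, it is unclear whether the record would appear there.

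These objections limit how often the rule matters. They do not reconcile 9.2 with 16.1.

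**Conclusion.** The concern holds as a boundary inconsistency. For a completely missing start date with an end date equal to first dose, 9.2 yields a non-TEAE flag, while 16.1 counts the first-dose day as on-treatment and the matching partial-date rules in 9.2 yield a TEAE. The number of affected records cannot be derived from the documents and may be zero. No visible efficacy result depends on this flag. The reason to act is direction: where the rule errs on a Day 1 reaction it understates treatment-emergent events, and the correction costs almost nothing.

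The conclusion assumes that first dose of study medication in 9.2 means the first randomised dose. If it meant the Visit 1 vehicle dose, the imputed start would be the Visit 1 date and the event would still be non-TEAE.

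The SAP does not say whether end dates are imputed before start dates. If they are, a subject dosed only on Day 1 whose event is marked not ongoing but has no end date would receive a Day 1 end date and meet the same exception.

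**What to change.** In the completely missing start-date rule of SAP 9.2, change 'on or before' to 'before'. A record with no start date and an end date equal to the first dose date then takes the first dose date as its onset and is a TEAE under 16.1. In the check above only that case changes; end dates of Day -1, Day 2 or missing keep their flags. The wording should make clear that first dose means the first randomised dose, because the one-word change does not repair the rule under the Visit 1 vehicle reading.

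The 1 January value can stay for events that ended before first dose. A later floor such as the consent date would not alter any of their TEAE flags.

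The cost is one word in the SAP and the matching line in the dataset specification, best made before unmasking. The same rule also dates concomitant medications, so that derivation should be checked when the line is edited. The downside is that an event which began before first dose and ended on Day 1 may be counted as a TEAE. In a safety summary that is the conservative direction.

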# 9.5 **Procedures for Reporting Adverse Events**

Adverse events that are ongoing at the end of the study visit will be followed. Phone calls will be placed with any subject who experiences an adverse event until the issue is resolved or the condition is considered ongoing and stable.

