12.2 Concomitant Medications and Procedures

Concomitant medications and procedures will be coded using World Health Organization Drug Dictionary (WHODrug) and summarized to the therapeutic drug class

and preferred name. If the second s

then the next lowest classification that is provided in the coding dictionary will be used. The preferred name will be defined as the active ingredient; if the active ingredient is not provided or includes more than two ingredients (e.g., multivitamins), then the drug name will be summarized as the preferred name. Any uncoded terms will be summarized under the

Concomitant medications are defined as those medications listed as having been taken (1) prior to initiation of study drug administration and continuing for any period of time following the first administration of study drug or (2) at any time following the first administration of study drug. Prior medications are defined as those medications as having been taken prior to initiation of study drug administration but not continuing any time following the first administration of study drug.

Concomitant medications will be summarized . Medications will be tabulated for each treatment group using frequencies and percentages.

At each level of subject summarization, a subject will be counted once if he/she reports one or more medications. Percentages will be based on the number of subjects in each treatment group. Listings of concomitant medications will be generated separately for ocular and non-ocular data.

13. Dosing Compliance and Treatment Exposure

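### SAP 9.2 moves a missing stop date to the last dose date without checking when the stop was recorded, so a medication already stopped at Visit 1 can be tabulated as concomitant

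*SAP*

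**What the plan says.** SAP 9.2 imputes start and end dates so that adverse events and medications can be flagged as treatment-emergent or concomitant. It has three end-date rules:

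- **Completely missing, not ongoing.** "If ongoing is 'No' then the missing end date will be imputed as the last dose date". No further condition applies.
- **Day missing.** "Dates with missing day only will be imputed as the last day of the month unless the month and year are the same". The comparison is with the last dose; where both match, the last dose day is used.
- **Day and month missing.** "Dates with both day and month missing will be imputed as 31 Dec unless the year is same as the year". Here too the comparison is with the last dose; where the year matches, the rule is: "missing day and month will be imputed as the last dose day and month of study medication".

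The only upper limit is death: "If the imputed date is after the date of death, then the end date will be set equal to the date of death". Imputed dates are used in derivations, and listings show the dates as recorded.

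SAP 12.2 counts a medication as concomitant if it was taken before study drug and continued for any time after the first administration, or was taken at any time after it. The counterpart reads: "Prior medications are defined as those medications as having been taken prior to initiation of study drug administration but not continuing any time following". Its reference point is again the first dose.

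The Visit 1 procedures in Protocol 8.3.1 include "Medical/Medication & Ocular History". SAP Table 1 places Visit 1 at Day -14 with a window of -16/+2 days, has no Day 0, and makes Day 1 the day of randomisation.

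**The concern.** An imputation rule should fill a gap without contradicting what is on record. If the site notes at Visit 1 that a medication has stopped but not when, the stop is known to be no later than Visit 1. The rule for a completely missing date ignores this and ends the medication on the last day of randomised dosing. The partial-date rules do the same when the month or year happens to match.

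The start-date rules do contain a consistency check: a completely missing start is not set to the first dose date if the end date is on or before it. The end-date rules have no equivalent.

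At stake is the accuracy of Tables 14.1.5.1 and 14.1.5.2 (ocular and non-ocular concomitant medications, ITT Population). Eligibility asks about past use of eye drops (inclusion 4; exclusions 4, 6 and 10), so stopped drops with vague dates are plausible Visit 1 entries. Shown as concomitant, they would suggest drop use during randomised treatment that did not occur, and the table would disagree with the dates in the listing.

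**Working it through.** The documents give no figure on this point to reproduce. The check applies the three rules to every possible date combination.

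**Inputs**
- Visit 1: Day -14, window -16/+2, so Day -30 to Day -12. With no Day 0 this is a gap g of 12 to 30 days before Day 1 (SAP Table 1).
- Last dose in a completer: Day 2. The protocol synopsis has one Day 2 dose and Protocol 7.1.4 has three; the date is the same either way.
- Concomitant: imputed end date after Day 1 (SAP 12.2). An imputed end on Day 1 itself is left out as unclear.
- Assumed: the start date is known and precedes Day 1; study medication means the randomised kit; Day 1 is spread evenly over a 365-day year (2021); the true stop is on the Visit 1 date.

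This gives 365 × 19 = 6,935 combinations of Day 1 and gap.

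**Completely missing, not ongoing.** The imputed end is Day 2 every time: 6,935/6,935 = 100%.

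**Day and month missing.** The end goes to Day 2 when Visit 1 and the last dose share a calendar year. For gap g this is 364 − g of the 365 Day 1 dates.
- At g = 14: 350/365 = 95.9%.
- Over all gaps: 19 × 364 − (12 + … + 30) = 6,916 − 399 = 6,517, and 6,517/6,935 = 94.0%.

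**Day missing.** The end goes to Day 2 when Visit 1 and the last dose, g + 1 days apart, share a month. A month of length L gives max(0, L − g − 1) such dates.
- At g = 12: 365 − 12 × 13 = 209, or 57.3%.
- At g = 14: 365 − 12 × 15 = 185, or 50.7%.
- At g = 30: 0.
- Over all gaps: 7 × 171 (31-day months) + 4 × 153 (30-day months) + 120 (February) = 1,929, and 1,929/6,935 = 27.8%. A further 221 (3.2%) fall on Day 1 itself.

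**Earlier stops.** If the medication stopped s days before Visit 1, replace g by g + s in the day-missing formula.
- 14-day gap, s from 1 to 7: 7 × 185 − 12 × 28 = 959 of 7 × 365 = 2,555, or 37.5%.
- 12 to 30 day gap, s from 1 to 7: 8,323/48,545 = 17.1%.
- 12 to 30 day gap, s from 1 to 30: 10,607/208,050 = 5.1%.

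Counting imputed ends on Day 1 as concomitant raises the last two to about 20% and 6%. Year-only dates stay at about 90% or more in these scenarios. Completely missing dates stay at 100%.

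**Two examples with a 14-day gap**

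| Visit 1 | Day 1 | Completely missing | Year only | Day missing |
|---|---|---|---|---|
| 22 Oct 2021 | 5 Nov 2021 | 6 Nov (wrong) | 6 Nov (wrong) | 31 Oct (prior, correct) |
| 6 Nov 2021 | 20 Nov 2021 | 21 Nov (wrong) | 21 Nov (wrong) | 21 Nov (wrong) |

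**With the end date capped at Visit 1:** 0 of 6,935 are misclassified under each rule.

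**The case against.** A late end date is a common conservative default: when in doubt, count the medication as concomitant. The rule is the same in both arms, listings keep the recorded dates, and protocol deviations are judged in a masked review, so a false appearance of prohibited use can be checked. The look-back periods in the exclusion criteria are redacted, so the documents do not show how many long-stopped drops would be entered at all. The SAP lists no table of prior medications, so a reclassified item leaves the summary tables. All of this stands and keeps the point small. It does not rescue the rule where the stop is already on record, because there is then no doubt to resolve conservatively.

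A reader might infer three stronger things.

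- *Every partial stop date goes to the last dose date.* It does so only when the month and year, or the year, match. Otherwise it becomes the end of the recorded month or year, which usually falls before Day 1 and gives the right status.
- *Adverse event durations, and so Table 14.3.4, are distorted.* Treatment-emergence rests on onset or worsening (SAP 16.1), and no visible text says how duration is derived or that imputed end dates feed it. Protocol 9.5 adds: "Adverse events that are ongoing at the end of the study visit will be followed", with phone calls until resolution or stability, which makes an unknown end day less likely.
- *An imputed end can fall before an event's start.* In a completer, adverse event collection ends at exit, which is on the last dose day, so this cannot happen. It would need a subject whose last dose and exit fall on different days.

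**Conclusion.** The point holds as a minor correction to a stated rule. In a completer, a medication recorded at Visit 1 as stopped is always counted as concomitant if its end date is completely missing. If the date is partial, this happens when the recorded month and year, or year, match the last dose. SAP 12.2 makes all of these prior medications. With the stop at Visit 1 the shares are 100%, 94% (year only) and 28% (day missing; 51% at the nominal gap), and the day-missing share drops to about 5% when stops range over the 30 days before Visit 1.

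These are shares of affected record types; the documents do not allow an estimate of how many such records there will be. They also rest on an even spread of Day 1 dates. If the last dose is on Day 1, the imputed end equals the first dose date and the status is unclear. The documented reach is the two descriptive concomitant-medication tables. Nothing links this flag to the PP Population or to any efficacy analysis, and treatment-emergence status is not shown to change.

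**What to change.** Add one bound to the end-date rules in SAP 9.2: an imputed medication end date may not be later than the visit (or, failing that, the eCRF entry date) at which the medication was first recorded as not ongoing. Items recorded as stopped at Visit 1 are then classed as prior. Keep the last-dose rule where no such date is available.

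Add a second sentence saying that this classification stands even if the partial start-date rules would give Day 1. Those rules, unlike the rule for a completely missing start, do not look at the end date.

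The cost is two sentences and a few lines of programming before database lock. Slightly fewer medications will be flagged as concomitant. The change depends on the recording visit or entry date being retrievable for each medication, which the documents do not confirm and which should be checked with data management first.
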